#### **7.2.5. Medical history**

Medical history findings (i.e. previous diagnoses, diseases or surgeries) meeting all criteria listed below will be collected:

- Not pertaining to the study indication.
- Start before signing of the informed consent.
- Considered relevant to the study.

#### **7.2.6. Blood Collection**

Patients who completed questionnaires over the telephone but are unable to return to UTMDACC will have their blood collected by their local physician and the results sent to the UTMDACC study team.

#### **7.2.7. Patient Remuneration**

After completion of the study assessments, patients will receive parking reimbursement for up to \$12.00 at baseline, Day 29 (± 3 days), and Day 57 (± 3 days) for a total of up to \$36.00.

### **7.3. Safety**

All subjects who receive at least one dose of study treatment will be valid for the safety analysis. All observations pertinent to the safety of the study treatment will be recorded and included in the final report.

Safety variables include the following: AEs, laboratory changes (complete blood counts, electrolytes, chemistry, and coagulation), changes in vital signs (blood pressure, heart rate, respiratory rate, and temperature) and ECG and, in some instances, changes in chest x-ray images, as produced at the investigator's discretion (e.g., for evaluation for pneumonia).

All AEs whether considered drug-related or not, will be reported in with a diagnosis, start/stop dates, action taken, whether treatment was discontinued, any corrective measures taken, outcome, and other possible causes. For all events, the relationship to treatment and the intensity of the event will be determined by the investigator.

This trial will use the NCI-CTCAE v4.0 criteria for assessment of toxicity and SAE reporting with regard to toxicity grade.

#### **7.3.1. Adverse events**

##### **Definitions**

###### **Definition of adverse event (AE)**

In a clinical study, an AE is any untoward medical occurrence (i.e. any unfavorable and unintended sign [including abnormal laboratory findings], symptom or disease) in a patient or clinical investigation subject after providing written informed consent for participation in the study. Therefore, an AE may or may not be temporally or causally associated with the use of a medicinal (investigational) product.

A surgical procedure that was planned prior to the start of the study by any physician treating the subject should not be recorded as AE (however, the condition for which the surgery is required may be an AE if worsens compared to baseline).

- Conditions that started before signing of informed consent and for which no symptoms or treatment are present until signing of informed consent are recorded as medical history (e.g. seasonal allergy without acute complaints).
- Conditions that started before signing of informed consent and for which symptoms or treatment are present after signing of informed consent, at *unchanged intensity*, are recorded as medical history (e.g. allergic pollinosis).
- Conditions that started or deteriorated after signing of informed consent will be documented as adverse events.

**Definition of serious adverse event (SAE)**

An SAE is classified as any untoward medical occurrence that, at any dose, meets any of the following criteria (a – f):

a. Results in death.

b. Is life-threatening.

The term 'life-threatening' in the definition refers to an event in which the patient was at risk of death at the time of the event, it does not refer to an event which hypothetically might have caused death if it were more severe.

c. Requires inpatient hospitalization or prolongation of existing hospitalization.

A hospitalization or prolongation of hospitalization will not be regarded as an SAE if at least one of the following exceptions is met:

- The admission results in a hospital stay of less than 12 hours.

- The admission is pre-planned. (i.e. elective or scheduled surgery arranged prior to the start of the study)

- The admission is not associated with an AE. (e.g. social hospitalization for purposes of respite care).

However, it should be noted that invasive treatment during any hospitalization may fulfill the criterion of 'medically important' and as such may be reportable as an SAE dependent on clinical judgment. In addition, where local regulatory authorities specifically require a more stringent definition, the local regulation takes precedence.

d. Results in persistent or significant disability / incapacity.

Disability means a substantial disruption of a person's ability to conduct normal life's functions.

e. Is a congenital anomaly / birth defect.

f. Is another medically important serious event as judged by the investigator.

**7.3.2. Classifications for adverse event assessment**

All AEs will be assessed and documented by the investigator according to the categories detailed below.

**7.3.2.1. Seriousness**

For each AE, the seriousness must be determined according to the criteria given in Section 7.3.1

**7.3.2.2. Intensity**

The intensity of the AE is classified according to the CTCAEv4.0. Grade refers to the severity (intensity) of the AE:

**CTCAEv4 Grade 1:** mild; asymptomatic or mild symptoms; clinical or diagnostic observations only; intervention is not indicated.

**CTCAEv4 Grade 2:** moderate; minimal, local, or noninvasive intervention is indicated; limiting to age-appropriate instrumental activities of daily living (ADL; instrumental ADL refers to preparing meals, shopping for groceries or clothes, using the telephone, managing money, etc).

**CTCAEv4 Grade 3:** Severe or medically significant but not immediately life threatening; hospitalization or prolongation of hospitalization is indicated; disabling; limiting to self-care ADL (self-care ADL refers to bathing, dressing and undressing, feeding self, using the toilet, taking medications, and not bedridden).

**CTCAEv4 Grade 4:** life-threatening consequences; urgent intervention is indicated.

**CTCAEv4 Grade 5:** death due to an AE.

### 7.3.2.3. Causal relationship

The assessment of the causal relationship between an AE and the administration of treatment is a clinical decision based on all available information.

The causality assessment should be done separately for each study treatment.

The assessment is based on the question whether there was a “reasonable causal relationship” to the study treatment in question.

Possible answers are “yes” or “no”.

An assessment of “no” would include:

1. The existence of a clear alternative explanation, e.g. mechanical bleeding at surgical site.

Or

2. Non-plausibility, e.g. the subject is struck by an automobile when there is no indication that the drug caused disorientation that may have caused the event; cancer developing a few days after the first drug administration.

An assessment of “yes” indicates that there is a reasonable suspicion that the AE is associated with the use of the study treatment.

Factors to be considered in assessing the relationship of the AE to study treatment include:

- The temporal sequence from drug administration: The event should occur after the drug is given. The length of time from drug exposure to event should be evaluated in the clinical context of the event.
- Recovery on drug discontinuation (de-challenge), recurrence on drug re-introduction (re-challenge):
- Subject's response after de-challenge or subjects response after re-challenge should be considered in the view of the usual clinical course of the event in question.
- Underlying, concomitant, intercurrent diseases: Each event should be evaluated in the context of the natural history and course of the disease being treated and any other disease the subject may have.
- Concomitant medication or treatment: The other drugs the subject is taking or the treatment the subject receives should be examined to determine whether any of them may be suspected to cause the event in question.
- The pharmacology and pharmacokinetics of the study treatment: The pharmacokinetic properties (absorption, distribution, metabolism and excretion) of the study treatment, coupled with the individual subject's pharmacodynamics should be considered.

#### **[Causal relationship to protocol-required procedure(s)]**

The assessment of a possible causal relationship between the AE and protocol-required procedure(s) is based on the question whether there was a “reasonable causal relationship” to protocol-required procedure(s).

Possible answers are “yes” or “no”.

#### **7.3.3. Action taken with study treatment**

Any action on study treatment to resolve the AE is to be documented using the categories listed below.

The study treatment action should be recorded separately for each study treatment.

- Drug withdrawn
- Drug interrupted
- Dose reduced
- Dose not changed
- Dose increased
- Not applicable
- Unknown

#### **7.3.3.1.1. Other specific treatment(s) of adverse events**

- None
- Remedial drug therapy

#### **7.3.3.1.2. Outcome**

The outcome of the AE is to be documented as follows:

- Recovered/resolved
- Recovering/resolving
- Recovered/resolved with sequelae
- Not recovered/not resolved
- Fatal
- Unknown

#### **7.3.3.2. Assessments and documentation of adverse events**

#### **7.3.3.3. Reporting of serious adverse events**

The definition of serious adverse events (SAEs) is given in Section 7.3.1.

Each serious adverse event must be followed up until resolution or stabilization, by submission of updated reports to the designated person. An isolated laboratory abnormality that is assigned grade 4, according to CTC definition, is not reportable as an SAE; unless the investigator assesses that the event meets standard ICH criteria for an SAE. CTC grade 4 baseline laboratory abnormalities that are part of the disease profile should not be reported as an SAE, specifically when they are allowed or not excluded by the protocol inclusion/exclusion criteria.

Throughout the course of the STUDY, the Principal Investigator and study personnel agree to comply with the obligations of adverse event reporting as set forth below, 'Safety Reporting Requirements' and with FDA regulations.

SPONSOR/ INSTITUTION is responsible for all the pharmacovigilance obligations and safety reporting pursuant to the applicable law and regulations in the country where the STUDY is performed.

Additionally, the SPONSOR/INSTITUTION shall immediately, within 24 hours at the latest, report to IRB/DSMB by fax or and/or email. **Safety Reporting Requirements**

The PRINCIPAL INVESTIGATOR must accept full responsibility for the trial and the safety of the subjects participating in the trial. The PRINCIPAL INVESTIGATOR is responsible for the ongoing safety evaluation of the study and shall provide to IRB/DSMB all Serious Adverse Events (SAEs) within 24 hours of the PRINCIPAL INVESTIGATOR'S awareness.

#### **Definitions:**

The following definitions, which are consistent with FDA and ICH regulations/guidance, will be used:

***Adverse Event (AE):***

An adverse event is any adverse event associated with the use of a drug in humans, whether or not considered drug related, including the following: An adverse event occurring in the course of the use of a drug in professional practice; an adverse event occurring from drug overdose whether accidental or intentional; an adverse event occurring from drug withdrawal; and any failure of expected pharmacological action.

***Serious Adverse Event (SAE):***

A serious adverse event includes any event that:

Results in death.

Is life-threatening.

NOTE: The term 'life-threatening' refers to an event during which the subject was at immediate risk of death from the adverse event. It does not refer to an event which hypothetically might have caused death if it had been more severe.

Requires inpatient hospitalization or prolongation of existing hospitalization.

NOTE: In general, hospitalization means that the subject has been detained at the hospital or emergency ward for observation or treatment that would not have been appropriate in the physician's office or out-patient setting. Complications that occur during hospitalization are AEs. If a complication prolongs hospitalization or fulfills any other serious criteria, the event is serious. When in doubt as to whether hospitalization occurred or was necessary, the AE should be considered serious. Hospitalization for elective treatment planned prior to study enrollment is neither an SAE nor an AE.

Results in persistent or significant disability or incapacity.

NOTE: The term disability means a substantial disruption of a person's ability to conduct normal life functions. This definition is not intended to include experiences of relatively minor medical significance such as uncomplicated headache, nausea, vomiting, diarrhea, influenza, and accidental trauma (e.g. sprained ankle) which may interfere or prevent everyday life functions but do not constitute a substantial disruption.

Is a congenital anomaly or birth defect.

Is an important medical event.

An event may be considered an important medical event when, based upon appropriate medical judgment, it may jeopardize the patient and may require medical or surgical intervention to prevent one of the outcomes listed in the definition. Examples of such medical events include allergic bronchospasm requiring intensive treatment in an

emergency room or at home, blood dyscrasias or convulsions that do not result in inpatient hospitalization, or the development of drug dependency or drug abuse.

***Adverse Drug Reaction (ADR):***

All noxious and unintended responses to a medicinal product related to any dose should be considered adverse drug reactions. The phrase “responses to a medicinal product” means in view of the investigator and/or company that a causal relationship between a medicinal product and an adverse event is at least a reasonable possibility and that the adverse event is associated with the use of the drug.

***Serious Adverse Drug Reaction (SADR):***

A Serious Adverse Drug Reaction is an event that meets any of the criteria for seriousness as previously defined and has a possible causal relationship to the study drug.

**Requirements for Reporting of Serious Adverse Events:**

**All SAEs must be reported to IRB/DSMB within 24 hours of the Principal Investigator's awareness and must include the following minimum information:**

- 1. The name and contact information of the reporter**
- 2. The name of the study drug(s)**
- 3. A description of the reported SAE**
- 4. A patient identified by one or more of the following:**

- a. Patient initials**
- b. Patient number**
- c. Knowledge that a patient who experienced the adverse event exists**
- d. Age**
- e. Sex**

**5. An investigator assessment of study drug causality. For studies with combination therapy, a separate causality assessment should be provided for each study drug.**

Additional data which would aid the review and causality assessment of the case include but are not limited to:

The date of onset

The severity

The time from administration of study drug(s) to start of the event

The duration and outcome of the event

Any possible etiology for the event

The final diagnosis or syndrome, if known

Action(s) taken, if any

For blinded studies, the Principal Investigator will provide the treatment assignment upon request for patients who experience SAEs. The Principal Investigator will provide the final treatment assignment immediately after the end of the study.

**Expedited Reporting of Other Safety Information:**

The Investigator/ Sponsor shall report to IRB/DSMB within 24 hours of the investigator's awareness of other events such as:

An adverse event related to study specific procedures

Any new and important event related to treatment with the study drug(s).

Any pregnancy during which a female patient was exposed to the study drug(s)

Any pregnancy in the partner of a male patient, where the male patient was exposed to study drug at the time of conception or conception occurred within two weeks of the last dose of study drug(s).

Any other relevant safety information including but not limited to reports on drug interaction, overdose, drug abuse or misuse, drug dependency, withdrawal syndrome, medication error, occupational exposure and lack of drug effect (LODE) occurring at any time during the treatment phase;

Any communication concerning safety related information to regulatory authorities or ethics committees including but not limited to:

- Development Safety Update Reports (DSUR) / relevant parts of IND reports for the STUDY;
- Any other safety related reports, issues and queries that are either raised by or communicated to regulatory authorities or ethics committees;

**The Investigator/Sponsor may report SAEs using:**

A MedWatch form available at <http://www.fda.gov/medwatch/>

**7.3.3.4. Expected adverse events due to Icosapent ethyl**

Below is the overview of the known side-effects reported by the use of study drug.

- **Musculoskeletal:** Arthralgia (2.3%)

### **7.3.4. Pregnancies**

The investigator must report to IRB/DSMB any pregnancy occurring in a study subject, or in his partner, during the subject's participation in this study. The report should be submitted within the same timelines as an SAE, although a pregnancy per se is not considered an SAE.

For a study subject, the outcome of the pregnancy should be followed up carefully, and any abnormal outcome of the mother or the child should be reported.

For the pregnancy of a study subject's partner, all efforts should be made to obtain similar information on course and outcome, subject to the partner's consent.

For all reports, the forms provided are to be used.

### **Progressive disease**

If progressive disease leads to signs and symptoms that meet the criteria for an SAE (i.e., hospitalization, disability, death, or important medical event), the signs and symptoms should be reported as an SAE and not the underlying progressive disease.

### **Death**

If any subject dies during the trial or within 30 days of the end-of-treatment visit, the investigator will inform IRB/DSMB and record the cause of death in detail (using the SAE Form) within 24 hours.

## **8. Statistical methods and determination of sample size**

The primary objective is to study is to determine the difference between the FACIT-F subscale score at baseline and at Day 57± 5 days, between patients who will receive either fish oil and PA and placebo and PA.

### **Interim Analysis Plan**

We plan to implement the Bayesian toxicity monitoring rule for severe toxicity (defined as any Grade 3 or 4 toxicity that is attributable to the FISH OIL treatment regimen as per NCI CTCAE V4 criteria) separately for each arm. We will stop the treatment arm if there is an 85% posterior probability to observe a larger than 30% severe toxicity rate in that arm, i.e.,  $Pr(P_{tox} > 0.3 | \text{data}) > 0.85$ , given that the prior of severe toxicity rate follows a beta distribution,  $\text{beta}(0.3, 0.7)$ . The cohort of monitoring will be every 5 patients starting from the first 10 patients. Given this rule, the accrual for a specific arm will be stopped if  $[\# \text{ severe toxicities}/\text{Total } \# \text{ of patients treated}] \geq 5/10, 7/15, 9/20, 11/25, 12/30, 13/32$ . Given these boundaries, we will have a 5%, 27% and 67% chance to stop an arm early if the true severe toxicity rate is 20%, 30% and 40% for that arm, respectively.

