### **4. Study Design**

#### **4.1 Study population**

Patients with advanced cancer will be recruited from UTMDACC. At UTMDACC, patients will be recruited from medical oncologists working in outpatient clinics, and in our own outpatient supportive care center. Patients will be screened for eligibility criteria. Patients who are eligible and who provide written informed consent to participate in this research study will be admitted to the double-blind phase of the study described below. Consent forms and assessments will be available and administered by the study-assigned research nurse. Feasibility: Is based on the prior successful accrual in similar symptom control trials by our group in these sites and great interest in Complementary and Alternative Medicine (CAM) in this population (48%).

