#### **6.4. Drug logistics and accountability**

All study drugs (Icosapent ethyl/Placebo) will be stored at the investigational site in accordance with Good Clinical Practice (GCP) and Good Manufacturing Practices (GMP) requirements and the instructions given by the clinical supplies department of the Institution and will be inaccessible to unauthorized personnel.

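### The toxicity stopping rule counts Grade 3 and 4 events but not Grade 5, so a related death can add nothing to the only numeric safety tally

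*Combined protocol and SAP*

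**What the plan says.** Section 8, Interim Analysis Plan, sets a Bayesian rule that is applied to each arm separately. The monitored event is severe toxicity, "defined as any Grade 3 or 4 toxicity that is attributable to the FISH OIL treatment regimen as per NCI CTCAE V4 criteria". An arm stops when the posterior probability that its severe toxicity rate exceeds 30% is above 0.85, under a Beta(0.3, 0.7) prior. Looks start at 10 patients and recur every 5. The boundaries are 5/10, 7/15, 9/20, 11/25, 12/30 and 13/32, and the stated chances of early stopping are 5%, 27% and 67% at true rates of 20%, 30% and 40%.

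Section 7.3.2.2 (Intensity) gives the grading scale. Grade 4 is the life-threatening category. Grade 5 is a grade of its own: "death due to an AE".

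Deaths also travel by other routes. Under the heading Death: "If any subject dies during the trial or within 30 days of the end-of-treatment visit, the investigator will inform IRB/DSMB", with the cause recorded, within 24 hours. Section 7.3.3.3 says the principal investigator "shall provide to IRB/DSMB all Serious Adverse Events (SAEs) within 24 hours" of becoming aware of them. Section 9 assigns data safety review to a DSMB, and Section 10 allows the study to end on safety findings.

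**The concern.** A rule for severe toxicity should count the most severe outcome. This one names two grades of a five-grade scale and stops short of the top one. It does not use an open-ended phrase such as Grade 3 or higher, and nothing elsewhere folds Grade 5 into Grade 4. Section 11.1 asks for strict adherence to the protocol's specifications, so the literal reading cannot simply be waved aside.

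The consequence is narrow. A patient who had a related Grade 3 or 4 event before dying is already in the numerator. Only a related death with no such earlier event is missed. When that happens, two arms with the same number of patients severely harmed by treatment can fall on opposite sides of a boundary. This matters because Section 8 contains the only safety criterion in the plan with a numeric limit. The other routes rely on case-by-case judgement, and the end-of-study toxicity tables by grade trigger no decision.

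**Working it through.** **Inputs from Section 8.** Prior Beta(0.3, 0.7); toxicity limit 0.30; posterior cut-off 0.85; looks at n = 10, 15, 20, 25, 30 and 32 per arm.

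**Step 1: reproduce the boundaries.** With x events in n patients the posterior is Beta(0.3 + x, 0.7 + n − x). The boundary is the smallest x for which Pr(p > 0.30) is above 0.85.

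| n | Boundary x | Posterior at x | Posterior at x − 1 |
|---|---|---|---|
| 10 | 5 | 0.890 | 0.720 |
| 15 | 7 | 0.900 | 0.773 |
| 20 | 9 | 0.911 | 0.812 |
| 25 | 11 | 0.922 | 0.843 |
| 30 | 12 | 0.867 | 0.767 |
| 32 | 13 | 0.890 | 0.804 |

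All six boundaries match the plan.

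**Step 2: reproduce the stopping chances.** Exact binomial recursion over the looks, dropping paths once they reach a boundary, with looks through 30: 4.58%, 26.94% and 66.51% at true rates of 20%, 30% and 40%. These round to the stated 5%, 27% and 67%. Adding the look at 32 gives 4.6%, 27.5% and 67.9%. The arithmetic is correct for the event as defined.

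**Step 3: one omitted death.** The last column of the table shows that at every look, one event fewer than the boundary puts the posterior below 0.85. An uncounted death therefore changes the decision when the full count sits exactly on the boundary. At n = 10, take 4 patients with related Grade 3/4 events and 1 related death without one:

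- as written, 4/10: Beta(4.3, 6.7), posterior 0.720, continue;
- with Grade 5 counted, 5/10: Beta(5.3, 5.7), posterior 0.890, stop.

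**Step 4: effect on the chance of stopping.** The documents give no severe or fatal toxicity rate, so the size depends on an assumption. Let the total related Grade 3–5 rate be p, and let d be the part that consists of deaths with no earlier counted event. The rule as written sees p − d; the corrected rule sees p. Looks through 30:

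| p | Grade 5 counted | As written, d = 1 point | Loss (points) | Loss if d = 2 points |
|---|---|---|---|---|
| 5% | 0.0065% | 0.0022% | 0.004 | 0.006 |
| 10% | 0.178% | 0.108% | 0.07 | 0.12 |
| 20% | 4.58% | 3.61% | 0.97 | 1.8 |
| 30% | 26.94% | 23.58% | 3.36 | 6.5 |
| 40% | 66.51% | 62.67% | 3.84 | 7.8 |

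Including the look at 32 changes these losses by at most 0.2 points.

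**Scale of the assumption.** One point in a 32-patient arm is 0.01 × 32 = 0.32 uncounted related deaths. At p = 5%, it means that 1 in 5 severe toxicities is fatal with no earlier counted event.

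**The case against.** The strongest reply is that this rule is not the tool for a related death, and that the trial has better ones. "All SAEs must be reported to IRB/DSMB within 24 hours", and deaths have their own notification on the same clock. The Bayesian rule first looks at 10 patients per arm and tracks tolerability against a 30% limit. In the 10-patient example, the related death and every Grade 3/4 event that met SAE criteria would already have gone to the IRB/DSMB. Related deaths also look unlikely: patients need Zubrod 0–1 and a life expectancy of at least 4 months, and the only expected drug effect listed in Section 7.3.3.4 is arthralgia at 2.3%. Any sensible team would count a death anyway.

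Most of that stands, and it is why the practical effect is very small. It does not make the definition right. The other routes carry no numeric limit, and a rule should not depend on its users overriding its own definition.

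A reader might infer three stronger points that the documents do not support.

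- *That the boundaries or stopping chances are wrong.* They reproduce.
- *That deaths go unmonitored, or that an arm with such a death would simply carry on.* That is true of the tally, not of the trial.
- *That the reference to the fish oil regimen makes the rule unworkable in the two placebo arms.* Patients are "admitted to the double-blind phase of the study described below", and Section 6.4 covers drug and placebo together: "All study drugs (Icosapent ethyl/Placebo) will be stored at the investigational site". Investigators can attribute events to the blinded capsule. The phrase is loose, but replacing it with study-drug wording could narrow the rule, because the tested regimen combines capsule and exercise and exercise-attributed events might then drop out.

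**Conclusion.** The definition is wrong as written: it leaves Grade 5 out of the severe-toxicity count, so a related death with no earlier counted Grade 3/4 event adds zero. It is probably a drafting slip, since no reason is given for the omission.

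This is a minor point. If uncounted deaths make up 1 percentage point of the total related severe-toxicity rate, the loss in stopping probability is under 0.1 point at total rates of 10% or less, and about 1 to 4 points at 20% to 40%. Nothing in the documents points to rates as high as 20%, and the 1-point figure is itself an assumption. The finding that the tally omits such deaths rests on the text alone and needs no assumption about rates.

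**What to change.** In the Interim Analysis Plan of Section 8, define the monitored event as *any Grade 3 or higher (Grade 3, 4 or 5) toxicity*. Leave the rest of that parenthesis, including the attribution wording, as it stands. Keep the Beta(0.3, 0.7) prior, the 30% limit, the 0.85 cut-off, the six boundaries and the stated stopping chances: they are functions of the event rate and hold for the wider event too. Because the attribution clause remains, deaths not attributed to the regimen still do not count.

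The cost is a one-phrase protocol change. It needs no new data, since intensity (including Grade 5) and causality are already recorded for every AE. The downside is a marginally higher chance of reaching a boundary, for example 4.6% instead of 3.6% at a 20% total rate if 1 point of it was uncounted deaths.
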